3.2 Number of subjects

Subjects for this study will be recruited from up to five clinical sites. A total of forty healthy evaluable subjects will participate in this study. Up to fifty subjects will be enrolled to account for projected dropout. It is anticipated that at least 10 subjects will be enrolled in the first year at UHCCM. An evaluable subject is one who has passed the inclusion and exclusion criteria; given informed consent; received and followed the treatment schedule, and has been adequately followed to establish valid endpoints of efficacy and tolerance.

3.3 Replacement of subjects

If a subject withdraws from the study prior to the 6 month follow-up, a replacement subject will be enrolled and will be assigned to the same drug or placebo group.

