2.0 OBJECTIVES

To quantify the improvement in scar appearance, we propose the use of two well-established methods of measurement: The Visual Analogue Scale (VAS) and the Patient and Observer Scar Assessment Scale (POSAS)^{6,7} The VAS will be used as the primary end point. It consists of a 10 point scale to assess global scar assessment. Scar photographic images are assessed by independent physicians, and previous studies have shown very high intrarater consistency. The POSAS consists of two numeric scales. One scale is completed by the patients, the other by the clinician. This scale is different than previous scales because it takes the patient’s input into consideration. It has good internal consistency and interobserver reliability.^{8,9}

2.1 Primary Objective:

To evaluate the efficacy of using aboBTX-A to improve wound healing prior to Mohs micrographic surgery and reconstruction for skin cancer as measured by the Visual Analogue Scale (VAS) at 6 weeks post surgery.

[figure not shown]
2.2 Secondary Objective:

- To evaluate efficacy of using aboBTX-A to improve wound healing prior to Mohs micrographic surgery and reconstruction for skin cancer as measured by the Patient and Observer Assessment Scale (POSAS) at week 1, 6, and 24.
- To evaluate the efficacy of using aboBTX-A to improve wound healing prior to Mohs micrographic surgery and reconstruction for skin cancer as measured by the Visual Analogue Scale (VAS) at week 1 and 24 post surgery.
- To evaluate patient satisfaction
- To evaluate safety (adverse events)

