12. Non-English speaking: These patients are excluded since translation of the informed consent into other languages is time-consuming and expensive as it requires a bona fide translator for the particular language of interest and this type of person may be difficult to locate.
13. House staff and students, medical students on a clerkship, and employees related to study personnel or who work for any study personnel, and members of the study team are not eligible to participate in this study as a subject.
14. The investigator feels that for any reason the subject is not eligible to participate in the study

4.3 **Inclusion of Women and Minorities**

Both men and women and members of all races and ethnic groups are eligible for this trial.

5.0 **REGISTRATION**

5.1 **Registration**

All subjects who have been consented will be registered in the OnCore Database. For those subjects who are consented, but not enrolled, the reason for exclusion will be recorded. All subjects from Collaborating Centers will also be registered through UHCMC and will be provided a study number by calling the telephone number of the Study Coordinator.

5.2 **Randomization**

Block randomization will be used to ensure equal or near equal numbers of subjects per study arm. Subjects from Collaborating Centers will be randomized upon receiving a study number from UHCMC.

6.0 **TREATMENT PLAN**

6.1 **Dysport**

Each patient will be able to receive up to 120 units of Dysport/placebo at the initial visit to treat the entire forehead area (the frontalis, procerus, and corrugator muscles) to insure cosmetic symmetry. Injections will be placed a minimum of 1.5cm above the orbital rim at the mid papillary line to minimize the risk of lid ptosis. The actual amount to be injected will be at the discretion of the Mohs surgeon based on his or her opinion of what amount is needed for sufficient wound paralysis and cosmetic symmetry.

Appropriate dose modifications for Dysport are described in Section 7.0.

Reported adverse events and potential risks of Dysport are described in Section 8.0

No investigational or commercial agents or therapies other than those described below may be administered with the intent to treat the patient's Mohs incision site.

6.2 **Definition of Dose-Limiting Toxicity**

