12.0 MEASUREMENT OF EFFECT

12.1 VAS: Visual Analog Scale. This is a 10 point scale to assess global scar assessment. At the conclusion of the study, photographs will be assessed in an independent and blinded fashion. After reviewing the photos of the wound at closure, at 6 weeks, and at 6 months, the participating raters will be asked to rate the cosmetic outcome at 6 weeks and 6 months on a 10-cm visual analog scale. The rater will be asked to assess the first patient together to establish a reference score for their respective further scores. Prior studies have shown very high intrarater consistency from VAS⁷. See statistical section for more information.

12.2 POSAS: Patient and Observer Scar Assessment Scale. The Patient and Observer Scar Assessment Scale (POSAS) consist of two numeric scales. One scale is completed by the patients, the other by the clinician. This scale is different than previous scales because it takes the patient's input into consideration. It has good internal consistency and interobserver reliability⁸⁻¹⁰. Patient POSAS will be collected at visit 2, 3, 4, and 5. Physician POSAS will be collected by each surgeon at visit 2, 3, 4, and 5. In addition, at the conclusion of the study, all four participating investigators will evaluate the photos of the wound at closure, at 6 weeks, and at 6 months for PSOAS scores in vascularity, pigmentation, thickness, and surface area. Relief and pliability will not be assessed as photographs do not allow for measurement of these values.

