13.2.1 Written Informed Consent

Provision of written informed consent must be obtained prior to any study-related procedures. The Principal Investigator will ensure that the subject is given full and adequate oral and written information about the nature, purpose, possible risks and benefits of the study as well as the subject's financial responsibility. Subjects will also be notified that they are free to discontinue from the study at any time. The subject will be given the opportunity to ask questions and allowed time to consider the information provided.

The original, signed written Informed Consent Form will be kept with the Research Chart in conformance with the institution's standard operating procedures. A copy of the signed written Informed Consent Form will be given to the subject.

Withdrawal of consent: Subjects may choose to discontinue their participation in the study at any time by notifying the PI. They will be asked to send a written letter to the PI listed on the informed consent. No further research data will be obtained nor clinical data entered into the research database. Data gathered until the time of withdrawal will be maintained.

Illiterate subjects: In the event that illiterate individuals who understand English present themselves as potential study participants and meet all inclusion/exclusion criteria, the consent form will be read to that individual in the presence of a witness and all questions answered. The study participant will sign the consent document by "making their mark" in the signature space. Both the person obtaining the consent (either the PI or his/her official delegate) and the witness will co-sign and date the consent form, noting that the informed consent process has taken place.

Non-English speaking patients, house staff and students, medical students on a clerkship, and employees related to study personnel or who work for any study personnel, and members of the study team are not eligible to participate in this study as a subject.

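### Section 3.3 puts a replacement in the withdrawn subject's arm instead of randomising, and Section 14 does not say that replaced subjects with a 6-week photograph stay in the primary analysis

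*Combined protocol and SAP*

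**What the plan says.** - **Replacement (3.3).** Withdrawal at any time before the 6-month visit triggers replacement, and "a replacement subject will be enrolled and will be assigned to the same drug or placebo group".
- **Allocation (5.2).** "Block randomization will be used to ensure equal or near equal numbers of subjects per study arm". Assignment is tied to central registration: "Subjects from Collaborating Centers will be randomized upon receiving a study number from UHCMC". The section does not mention replacements, or who looks up the withdrawn subject's arm.
- **Endpoints (2.1, 2.2).** The primary objective is efficacy "as measured by the Visual Analogue Scale (VAS) at 6 weeks post surgery". A secondary objective is efficacy "as measured by the Visual Analogue Scale (VAS) at week 1 and 24 post surgery".
- **Target (3.1, 3.2).** Forty *evaluable* subjects, with enrolment up to fifty. *Evaluable* requires meeting the entry criteria and consenting. It also requires two things known only after randomisation: keeping to the treatment schedule and being followed well enough.
- **Analysis (14.1.3).** Each patient's VAS is the mean of four physicians' scores, compared by the Wilcoxon rank sum test. No analysis set, missing-data rule or rule for replaced subjects is given, and the word *evaluable* does not appear.
- **Rating (12.1).** At study end, "photographs will be assessed in an independent and blinded fashion". Raters look at the closure, 6-week and 6-month photographs before scoring.
- **Withdrawal of consent (13.2.1).** "No further research data will be obtained nor clinical data entered into the research database", but "Data gathered until the time of withdrawal will be maintained".

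**The concern.** There are two problems of unequal weight.

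First, a replacement's arm is fixed by an earlier subject's arm. Anyone who knows or guesses the earlier assignment knows the next one before enrolling the new subject. Guessing is conceivable, because the toxin stops muscle contraction and is injected 2 to 4 weeks before surgery. That is an inference from Sections 1.1 and 11.1, not something the plan reports.

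Second, and more important, replacement continues to month 6 although the primary measurement is complete at week 6. Replacing a subject suggests that the subject no longer counts toward the forty. If that meant leaving the primary analysis, outcomes already photographed would be discarded for reasons arising after randomisation. Should poor scars make withdrawal more likely in one arm, the arm difference would shift. Filling the place with a new subject in the same arm restores the head-count and hides the loss without correcting it.

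**Working it through.** **Inputs.** From 14.1.1 and 14.1.2: 20 per group, effect size 1.0, two-sided 5% test, stated power 80%, SD 1.4 to 2.2, minimal important difference 1.5 points, dropout 5-10%, Wilcoxon efficiency 95%, 25 enrolled per group. From 11.1: Visit 1 is 2 to 4 weeks before surgery. Withdrawal patterns are not in the documents and are assumed below. All tests use the 5% level of 14.1.2.

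**The plan's own figure.** A two-sided 5% t-test with 20 per group at effect size 1.0 has 86.9% power, not 80%; 17 per group gives 80.7%. With 95% efficiency the power is 85.1%, and simulation of the Wilcoxon test gives 85.0%. The stated 80% is conservative at this effect size, and 85% is the baseline below.

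**How many replaced subjects already have the primary photograph?** Assume that withdrawal is uniform from Visit 1.
- Taking the last visit as week 24: 18/28 = 64% to 18/26 = 69% of follow-up lies after week 6.
- Taking 6 months as 26 weeks: 20/30 = 67% to 20/28 = 71%.
- Number affected: 40 × 5% × 0.64 = 1.3 up to 50 × 10% × 0.71 = 3.6, so about 1 to 4 subjects.

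**Same-arm rule alone.** If 2 of 20 in one arm are replacements with a prognosis 0.5 SD better (assumption), the shift is 2/20 × 0.5 = 0.05 SD. That is 0.05 × 1.4 = 0.07 to 0.05 × 2.2 = 0.11 points. Type I error stays at 5.0%.

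**If replaced subjects were dropped.** Simulation with normal scores of unit SD and a two-sided Wilcoxon test. Two of 20 placebo subjects are removed and replaced by fresh draws from the same arm.

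| Withdrawal pattern (assumed) | Shift | Type I error | Power at 1.0 |
|---|---|---|---|
| No loss | 0 | 4.8% | 85% |
| Correlation 0.5 with scar score | 0.08 SD | 5.8% | 80% |
| The two worst scars | 0.16 SD | 8.5% | 76% |

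- In VAS points, the middle row is 0.08 × 1.4 = 0.11 to 0.08 × 2.2 = 0.18, or 7% to 12% of 1.5. The last row is 0.164 × 1.4 = 0.23 to 0.164 × 2.2 = 0.36, or 15% to 24%.
- Direction follows the arm that loses subjects. In the extreme case with placebo losses, false claims for drug fall from 2.4% to 1.0% and false claims for placebo rise from 2.4% to 7.4%. With drug-arm losses, false claims for drug rise to 7.5%.
- One worst-scar loss in each arm: the shift cancels, type I error is about 6%, and power does not fall.
- At 25 per arm, where no-loss power is 91.7%: correlation 0.5 gives 0.07 SD, 5.5% and 88.5%; the extreme case gives 0.14 SD, 7.6% and 86%.

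**If replaced subjects with a photograph are kept.** Under one-sided, scar-related withdrawal, simulated type I error is 4.5% to 4.8% with no material shift.

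**What same-arm matching buys.** A 22/18 split has the precision of 2/(1/22 + 1/18) = 19.8 per arm, against 20 for an exact split.

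**The case against.** The strongest reply is that nothing in the plan says replaced subjects are dropped. Section 14.1.3 speaks of each patient, which is naturally read as everyone with ratings, and *evaluable* appears only with the recruitment target. Registration is central, photographs are rated blind, and the arm a replacement inherits was itself randomised. The larger figures need several assumptions together: exclusion, loss from one arm only, and loss driven entirely by scar quality. The one power figure below 80% also uses 20 per arm, while 14.1.2 enrols 25.

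Much of this stands. It limits the size of the point but does not settle who is analysed, because each patient is not a defined set once some patients have been replaced.

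A reader might infer more than the documents support:
- *That concealment or blinding has failed.* Central numbering and blinded rating are specified. Only a route to prediction is shown.
- *That the primary analysis is restricted to evaluable subjects, so type I error is 8.5%.* Section 14 never says so, and 8.5% belongs to the extreme pattern only.
- *That replacement can simply be abolished because 25 per group are enrolled.* Sections 3.1 and 3.2 can be read as enrolling 40 and adding up to 10 for dropout. Without those additions, 20 × 0.90 = 18 to 20 × 0.95 = 19 per arm would remain, below 20/0.95 = 21.1.
- *That 13.2.1 forbids scoring a withdrawn subject's photograph.* A stored photograph is most naturally data already gathered. A line of confirmation is enough.

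**Conclusion.** The point holds as a should-fix matter of allocation and analysis-set wording, with medium confidence. Section 3.3 states a rule that bypasses the block randomisation. By itself the effect is small: 0.05 SD under an assumed prognostic difference, with no inflation of type I error.

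The more consequential gap is the unstated status of replaced subjects who already have the primary photograph, perhaps 1 to 4 people if withdrawal is uniform over time. The bias is conditional on their being dropped and on scar-related withdrawal concentrated in one arm. For two placebo losses at 20 per arm, a moderate pattern gives about 0.08 SD, type I error near 6% and power of 80%. The outer bound is 0.16 SD, 8.5% and 76%. Because VAS scores are produced only at study end, leaving the set undefined allows the choice to be made after withdrawals are known.

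**What to change.** (a) In 3.3, delete the same-arm rule and give any additional subject the next number on the concealed block list, within the 50 planned.

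(b) In 14.1.3, state that the primary analysis includes every randomised subject with a 6-week photograph, in the assigned arm, whether or not the subject was later replaced or has a 6-month photograph. State that *evaluable* is a recruitment target only. Report subjects without a 6-week photograph by arm and reason. Add a line to the rating instructions in 12.1 for subjects with no 6-month photograph.

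(c) Minor: confirm in 13.2.1 that a photograph taken before withdrawal counts as data gathered and may be scored at study end, with matching consent wording if needed.

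**Limit.** This recovers only subjects lost after week 6, roughly two thirds of withdrawals if they are uniform over time. Earlier losses stay missing.

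**Cost.** Protocol and SAP wording, one rating instruction, and possibly a small consent change with IRB review. No subjects beyond the 50 are needed. The arms may not be exactly equal, but the loss of precision from a split such as 22/18 is negligible.

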3.4 Expected Duration of Subject Participation

3.4.1 Duration of Therapy

Study subjects will be given a one time treatment with Dysport at their first visit. This one time injection of Dysport is expected to cause an effect for approximately 3 months.

3.4.2 Duration of Follow-up

Patients will be followed for toxicity and effect for 6 months after treatment the one time treatment with Dysport. If there are adverse events the clinical course of each event will be followed until resolution, stabilization, or until it has been determined that the study treatment or participation is not the cause. Serious adverse events that are still ongoing at the end of the study period will necessitate follow-up to determine the final outcome. Any serious adverse event that occurs after the study period and is considered to be possibly related to the study treatment or study participation will be recorded and reported immediately.

4.0 PATIENT SELECTION

4.1 **Inclusion Criteria:**

Patients must meet all of the following inclusion criteria to be eligible for enrollment:

1. Adults 18 years or older.
2. Ability to understand the risks, benefits, and alternative to participation and give informed consent
3. Have biopsy proven skin cancer on the medial forehead that is amenable to Mohs surgery. Medial forehead is defined as the area superiorly from the hairline, inferiorly at the eyebrow, and laterally to the tip of the lateral brow (see diagram).
4. Undergoing elective reconstruction of biopsy proven skin cancer that is amenable to Mohs surgery with defect size measuring 1.0 cm or greater
5. If female, not currently pregnant, no potential for pregnancy, or if of child-bearing age, must agree to use adequate contraception (e.g., hormonal or barrier method of birth control; abstinence) for 30 days after the last dose of study drug. A negative urine pregnancy test is required at study entry for female subjects of childbearing potential: a woman is considered to be of child bearing potential unless she has had a tubal ligation, total hysterectomy, bilateral oophorectomy, or is postmenopausal (without a menstrual period for at least one year)
6. Agrees to not use disallowed concomitant medications (retinoids)

4.2 **Exclusion Criteria**

The presence of any of the following will exclude a patient from study enrollment.

1. Pregnant women, women who are breastfeeding, or women of child bearing age who are unwilling to use adequate contraception (described above) during the study period
2. Current or past history of a neuromuscular disease (such as myasthenia gravis, amyotrophic lateral sclerosis, Eaton-Lambert syndrome)
3. Currently taking aminoglycosides or other agents interfering with neuromuscular transmission (e.g., curare-like agents)
4. History of radiation therapy or chemotherapy
5. History of keloid or other hypertrophic scar formation
6. Current or past history of scleroderma
7. Has used botulinum toxin in the forehead area within one year.
8. Has significant resting eyebrow ptosis
9. Has used any topical retinoids to the forehead area within the past 4 weeks
10. Undergo any scar revision procedure for the duration of the study including intralesional kenalog, laser treatment, and/or scar revision surgeries
11. Any hypersensitivity to any component of abobotulinumtoxinA (i.e. cow milk protein) or any previous hypersensitivity to any botulinum toxin A or related product.
12. Non-English speaking: These patients are excluded since translation of the informed consent into other languages is time-consuming and expensive as it requires a bona fide translator for the particular language of interest and this type of person may be difficult to locate.
13. House staff and students, medical students on a clerkship, and employees related to study personnel or who work for any study personnel, and members of the study team are not eligible to participate in this study as a subject.
14. The investigator feels that for any reason the subject is not eligible to participate in the study

4.3 **Inclusion of Women and Minorities**

Both men and women and members of all races and ethnic groups are eligible for this trial.

5.0 **REGISTRATION**

5.1 **Registration**

All subjects who have been consented will be registered in the OnCore Database. For those subjects who are consented, but not enrolled, the reason for exclusion will be recorded. All subjects from Collaborating Centers will also be registered through UHCMC and will be provided a study number by calling the telephone number of the Study Coordinator.

5.2 **Randomization**

Block randomization will be used to ensure equal or near equal numbers of subjects per study arm. Subjects from Collaborating Centers will be randomized upon receiving a study number from UHCMC.

6.0 **TREATMENT PLAN**

6.1 **Dysport**

Each patient will be able to receive up to 120 units of Dysport/placebo at the initial visit to treat the entire forehead area (the frontalis, procerus, and corrugator muscles) to insure cosmetic symmetry. Injections will be placed a minimum of 1.5cm above the orbital rim at the mid papillary line to minimize the risk of lid ptosis. The actual amount to be injected will be at the discretion of the Mohs surgeon based on his or her opinion of what amount is needed for sufficient wound paralysis and cosmetic symmetry.

Appropriate dose modifications for Dysport are described in Section 7.0.

Reported adverse events and potential risks of Dysport are described in Section 8.0

No investigational or commercial agents or therapies other than those described below may be administered with the intent to treat the patient's Mohs incision site.

6.2 **Definition of Dose-Limiting Toxicity**

Not applicable to this study as a single dose of dysport/placebo will be administered. There will be no dose escalations. Reported adverse events and potential risks of Dysport are described in Section 8.0.

6.3 **General Concomitant Medications and Supportive Care Guidelines**

Aminoglycosides or other agents interfering with neuromuscular transmission (e.g., curare-like agents) may potentiate the effects of Botox. Patients currently receiving these agents are excluded from the study.

Using currently available analytical technology, it is not possible to detect *Dysport* in the peripheral blood following intramuscular injection at the recommended doses. Dysport is not known to interfere with cytochrome P450.

Patients should receive full supportive care, including transfusions of blood and blood products, cytokines, antibiotics, antiemetics, etc when appropriate.

6.4 **Duration of Therapy**

Study subjects will be given a one time treatment with Dysport at their first visit. This one time injection of Dysport is expected to cause an effect for approximately 3 months.

